6.1.2. Primary Immunogenicity Endpoints

6.1.2.1. Primary BNT162b2 Immunogenicity

- Full-length S-binding IgG levels 1 month after vaccination with BNT162b2.

6.1.2.1.1. Main Analyses

- Estimands: GMR of full-length S-binding IgG levels 1 month after vaccination with BNT162b2 (at Visit 1) in the coadministration group to the IgG levels 1 month after vaccination with BNT162b2 (at Visit 2) in the separate-administration group ([Section 2.1](#)).
- Analysis set: Evaluable BNT162b2 immunogenicity population, all-available immunogenicity population (as applicable) ([Section 4](#)).
- Analysis time point: 1 Month after vaccination with BNT162b2.
- Analysis methodology: The GMR and the associated 2-sided 95% CIs will be calculated using the statistical methods described in [Section 5.2.2.1](#). Noninferiority will be declared if the lower bound of the 2-sided 95% CI for the GMR is greater than 0.67 ([Section 5.1.1](#)).
- Intercurrent events and missing data: Serology data deemed unevaluable because of noncompliance with the key protocol criteria will be excluded. Missing data will not be imputed.
- Reporting results: The adjusted GMR and 2-sided 95% CI will be calculated based on the primary approach using a linear regression model that includes vaccine group, age group, and baseline (Visit 1 for the coadministration group and Visit 2 for the separate-administration group) full-length S-binding IgG levels as factors. The unadjusted GMR and the associated 2-sided 95% CI will also be provided.

6.1.2.1.2. Supplemental Analyses

Supplemental analysis will be performed in participants without evidence of SARS-CoV-2 infection through 1 month after BNT162b2 vaccination. The unadjusted GMR and the associated 2-sided 95% CI will be provided. The designation of “without evidence of SARS-CoV-2 infection through 1 month after BNT162b2 vaccination” is given to participants who have no serological or virological evidence (prior to the 1-month post-BNT162b2 vaccination blood sample collection) of SARS-CoV-2 infection (ie, N-binding antibody negative before study vaccination and at the 1-month post-BNT162b2 vaccination visit, and no reported SARS-CoV-2 infection or COVID-19 through the 1-month post-BNT162b2 vaccination blood sample collection) and have no medical history of SARS-CoV-2.

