4. ANALYSIS SETS (POPULATIONS FOR ANALYSIS)

Analysis populations are defined for the statistical analysis of safety and immunogenicity results in the table below. Data for all participants will be assessed to determine if participants meet the criteria for inclusion in each analysis population prior to unblinding and releasing the database, and classifications will be documented per standard operating procedures.

Population	Description
Enrolled	All participants who have a signed ICD.
Randomized	All participants who are assigned a randomization number in the IRT system.
Evaluable BNT162b2 immunogenicity	All eligible randomized participants who receive all vaccinations at Visit 1 as randomized (coadministration group) or receive all vaccinations at Visit 1 and Visit 2 as randomized (separate-administration group), have at least 1 valid and determinate full-length S-binding IgG or SARS-CoV-2 neutralizing titer result from the blood sample collected within the predefined window (within 28-42 days after receipt of BNT162b2) at Visit 2 (coadministration group) or at Visit 3 (separate-administration group), have no reported COVID-19 or new SARS-CoV-2 infection after Visit 1 and through 1 month after BNT162b2 vaccination (Visit 2 for the coadministration group and Visit 3 for the separate-administration group), and have no other important protocol deviations as determined by the clinician.
Evaluable SIIV immunogenicity	All eligible randomized participants who receive all vaccinations at Visit 1 as randomized, have at least 1 valid and determinate HAI titer or H3N2-neutralizing antibody titer result from the blood sample collected within the predefined window at Visit 2 (within 28-42 days after receipt of SIIV), and have no other important protocol deviations as determined by the clinician.
All-available immunogenicity	All randomized participants who have at least 1 valid and determinate immunogenicity result after receiving study intervention.
Safety	All participants who receive any of the study intervention.

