5.2.2.1. Geometric Mean Ratios

Model-Based

As the primary approach (only for primary endpoints), the GMRs and associated 95% CIs will be calculated by exponentiating the difference in LS means of the 2 vaccine groups and the corresponding CIs based on analysis of logarithmically transformed assay results using a linear regression model that includes vaccine group, age group, and corresponding baseline assay results as factors.

Unadjusted

The GMRs will be calculated as the difference in the means of logarithmically transformed assay results between 2 vaccine groups and exponentiating the difference. The associated 2-sided 95% CIs will be obtained by calculating CIs using Student's t distribution for the mean difference of the logarithmically transformed assay results and exponentiating the confidence limits.

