6.2. Secondary Endpoints

6.2.1. Secondary BNT162b2 Immunogenicity Endpoints

6.2.1.1. Full-Length S-Binding IgG Levels

6.2.1.1.1. Main Analysis

- Estimands:
 - a. GMCs of full-length S-binding IgG levels before vaccination and 1 month after vaccination with BNT162b2 ([Section 2.1](#)).

- b. GMFRs of full-length S-binding IgG levels and SARS-CoV-2 neutralizing titers from before vaccination to 1 month after vaccination with BNT162b2 ([Section 2.1](#)).
- Analysis set: Evaluable BNT162b2 immunogenicity population, all-available immunogenicity population (as applicable) ([Section 4](#)).
- Analysis time point: Before vaccination (Visit 1 for the coadministration group and Visit 2 for the separate-administration group) and 1 month after vaccination with BNT162b2.
- Analysis methodology: The GMCs and the associated 2-sided 95% CIs at before vaccination and 1 month after vaccination with BNT162b2 will be provided for each vaccine group using the statistical methods described in [Section 5.2.2.2](#). The GMFRs and the associated 2-sided 95% CIs from before vaccination to 1 month after vaccination with BNT162b2 will be provided for each vaccine group using the statistical methods described in [Section 5.2.2.3](#).
- Intercurrent events and missing data: Serology data deemed unevaluable because of noncompliance with the key protocol criteria will be excluded. Missing data will not be imputed.
- Reporting results: GMCs and the associated 2-sided 95% CIs will be provided for each vaccine group at before vaccination and 1 month after vaccination with BNT162b2. GMFRs from before vaccination to 1 month after vaccination with BNT162b2 and the associated 2-sided 95% CIs will be provided for each vaccine group.

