6.4. Subset Analyses

Subgroup analyses based on age group, sex, race (if appropriate), and racial designation, as well as baseline SARS-CoV-2 status (based on N-binding antibody results at Visit 1 before vaccination and medical history of SARS-CoV-2), will be performed on all primary safety and immunogenicity endpoints (as supplemental analyses).

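### The infection-free supplemental analysis of S-binding IgG gives only an unadjusted GMR, so the adjusted primary estimate has no explicitly planned counterpart in that set

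*SAP*

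**What the plan says.** SAP 6.1.2.1.1 sets out two estimates for S-binding IgG 1 month after BNT162b2. The primary one is an adjusted GMR "using a linear regression model that includes vaccine group, age group, and baseline" S-binding IgG. The second follows directly: "The unadjusted GMR and the associated 2-sided 95% CI will also be provided". The baseline is the pre-BNT162b2 sample, taken at Visit 1 in the coadministration group and at Visit 2 in the separate-administration group.

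SAP 6.1.2.1.2 takes the same endpoint in participants with no serological, virological or medical-history evidence of infection through the endpoint sample. For them it says only: "The unadjusted GMR and the associated 2-sided 95% CI will be provided".

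Three other places bear on the point.

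- SAP 5.2.2.1 introduces the model-based GMR with "As the primary approach (only for primary endpoints". S-binding IgG is a primary endpoint (SAP 3.1.2), so this limit does not explain why the model is absent from 6.1.2.1.2.
- SAP 6.4 plans analyses by baseline SARS-CoV-2 status, among other factors, which "will be performed on all primary safety and immunogenicity endpoints (as supplemental analyses". It does not say whether the GMRs are adjusted.
- SAP 4 already requires the evaluable BNT162b2 population to "have no reported COVID-19 or new SARS-CoV-2 infection after Visit 1 and through 1 month after BNT162b2 vaccination".

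**The concern.** The SAP's primary model contains no term for infection. The question of whether the primary result holds in people untouched by infection therefore falls to 6.1.2.1.2 and the 6.4 subsets. A reader will naturally place the supplemental estimate beside the adjusted primary GMR. Those two figures differ in population and in estimator, so a gap between them could come from either.

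Two things are lost by leaving the model out. One is precision, because baseline antibody usually predicts post-vaccination antibody and the infection-free set is smaller than the evaluable set. The other is correction for baseline. Pre-BNT162b2 IgG is sampled about a month later, and after SIIV, in the separate-administration group, so the arms' baselines may differ by design as well as by chance. The main analysis corrects for that difference and the supplemental one does not.

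**Working it through.** **1. The plan's own figure.** Inputs from Protocol 9.5: SD 1.05 on the ln scale, 450 evaluable per group, true GMR 0.9, margin 0.67, 1-sided alpha 0.025.

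- SE = 1.05 × √(2/450) = 0.0700
- Effect = ln(0.9/0.67) = 0.2951
- 0.2951/0.0700 − 1.960 = 2.255, so power = 98.8%

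This matches the stated 98.8%. The product over the five coprimary endpoints also reproduces the stated 90.7% (90.8% by normal approximation, 90.7% by noncentral t). No stated figure is in dispute.

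**2. Availability of the covariates.** Age group is a stratification factor (SAP 2.2). Pre-BNT162b2 IgG is already summarised in both arms: SAP 6.2.1.1.1 gives its time points as "Before vaccination (Visit 1 for the coadministration group and Visit 2 for the separate-administration group) and 1 month after vaccination with BNT162b2". Nothing more has to be collected.

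**3. Precision.** Let ρ be the within-arm correlation between baseline and post-vaccination ln IgG. The documents do not give it, so 0.3 to 0.7 is an assumed range. Adjustment multiplies the SE by √(1−ρ²), which is equivalent to multiplying the sample size by 1/(1−ρ²).

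| ρ | SE factor | Sample-size factor |
|---|---|---|
| 0.3 | 0.95 | 1.10 |
| 0.5 | 0.87 | 1.33 |
| 0.7 | 0.71 | 1.96 |

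The size of the infection-free set is not given either, so a range is shown. With SD 1.05 and an observed GMR of 0.9, the lower 95% limit is 0.9 × exp(−1.96 × 1.05 × √(1−ρ²) × √(2/n)).

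| n per arm | Unadjusted | ρ = 0.3 | ρ = 0.5 | ρ = 0.7 |
|---|---|---|---|---|
| 300 | 0.761 | 0.767 | 0.778 | 0.798 |
| 225 | 0.741 | 0.748 | 0.761 | 0.784 |
| 150 | 0.710 | 0.717 | 0.733 | 0.760 |
| 100 | 0.673 | 0.682 | 0.699 | 0.731 |

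At 225 per arm the ln-scale half-width is 1.96 × 1.05 × √(2/225) = 0.194 unadjusted. Adjusted, it is 0.185, 0.168 or 0.139.

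For scale only, take a true GMR of 0.9 and the chance that the lower limit clears 0.67. At 300 per arm it rises from 93.1% to 95.0, 97.8 or 99.8%. At 225 it rises from 84.6% to 87.8, 93.1 or 98.7%. At 150 it rises from 68.2% to 72.3, 80.3 or 92.6%. No test is attached to this analysis.

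**4. Baseline difference.** If the arms' pre-BNT162b2 geometric means have ratio b and the regression slope on ln baseline is s, then unadjusted GMR ÷ adjusted GMR = b^s, leaving aside age group. Both inputs are assumptions.

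- s = 0.5: b = 0.9 gives 0.95, and b = 1.1 gives 1.05.
- s = 0.3 to 0.7: b = 0.9 gives 0.97 to 0.93, and b = 1.1 gives 1.03 to 1.07.

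**5. Which comparisons the SAP secures.**

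| Estimator | Evaluable set (6.1.2.1.1) | Infection-free set (6.1.2.1.2) |
|---|---|---|
| Unadjusted | planned | planned |
| Adjusted (primary) | planned | not stated |

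The baseline-negative subset under 6.4 would hold nearly the same people as the infection-free set, but its estimator is left open.

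**The case against.** The strongest reply is that the SAP is coherent as it stands. The unadjusted main GMR is prespecified, so unadjusted main against unadjusted supplemental is a comparison with one estimator and two populations. That is correct. A reader might infer that no like-for-like comparison exists, or that a discrepancy could never be traced to infection status. The documents do not support either inference.

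A reader might also take this to be the only GMR analysis free of infection through the endpoint. That goes too far. The evaluable population already excludes new infections, and 6.4 plans a baseline-negative subset close to the infection-free set.

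Nor is selection after randomisation peculiar to this analysis. By the visit windows, follow-up for infection runs 28 to 42 days after Visit 1 in the coadministration group and 56 to 84 days in the other (28 + 28 to 42 + 42). The definition of the evaluable population carries the same inequality, so the adjusted main analysis shares it. Adjustment would not cure it, and in the separate-administration group the covariate is itself measured after randomisation.

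Baseline IgG is not discarded either: it enters the primary model and the secondary GMC and GMFR summaries.

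Finally, the correlation and subset sizes are assumptions, and SD 1.05 comes from post-Dose 2 data in other studies. At ρ = 0.3 the gain is only about 5% in SE. All of this stands. None of it supplies the missing estimate, since 6.4 does not commit to a model.

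**Conclusion.** The point holds as a minor improvement. The SAP does not explicitly plan the sponsor's own primary estimator in infection-free participants, although the covariates are in hand. The unadjusted estimate has an SE about 1.05 to 1.40 times the adjusted one (1/0.954 to 1/0.714) for correlations of 0.3 to 0.7. It also carries any baseline difference between arms into the GMR, about 5% either way for a baseline ratio of 0.9 or 1.1 at a slope of 0.5. Correlation, slope, baseline ratio and subset size are assumptions, not document figures.

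A reader might infer a threat to the noninferiority conclusion. There is none: the 0.67 criterion belongs to the main analysis, and 6.1.2.1.2 has no decision rule.

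**What to change.** Add to SAP 6.1.2.1.2, in words such as: *The GMR with its 95% CI will be estimated by the Section 6.1.2.1.1 model (vaccine group, age group, log pre-BNT162b2 S-binding IgG), with the unadjusted estimate shown beside it.* Report the number of participants in each estimate, since the adjusted one needs a pre-vaccination result.

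In SAP 6.4, state that GMRs for the primary immunogenicity endpoints use the same modelling approach with the corresponding baseline assay result, dropping age group as a factor where age defines the subset.

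The cost is a sentence in each section and some further model runs. No new data are needed. Because neither the primary endpoint nor its main analysis changes, the rule in Protocol 9 that major changes to these go into a protocol amendment would not apply.

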6.1.2.2. Primary SIV Immunogenicity

- Strain-specific HAI titers (or H3N2-neutralizing antibody titers if H3N2-HAI titers cannot be obtained) 1 month after vaccination with SIV.

6.1.2.2.1. Main Analyses

- Estimands: GMR of the strain-specific HAI (or H3N2-neutralizing antibody) titers 1 month after vaccination with SIV in the coadministration group to the corresponding HAI (or H3N2-neutralizing antibody) titers in the separate-administration group ([Section 2.1](#)).
- Analysis set: Evaluable SIV immunogenicity population, all-available immunogenicity population (as applicable) ([Section 4](#)).
- Analysis time point: 1 Month after vaccination with SIV.
- Analysis methodology: For each influenza strain, the GMRs and the associated 2-sided 95% CIs will be calculated using the statistical methods described in [Section 5.2.2.1](#). Noninferiority for a strain will be declared if the lower bound of the 2-sided 95% CI for the GMR is greater than 0.67. The primary SIV immunogenicity objective of the study will be achieved if the noninferiority is met for each of the influenza strains ([Section 5.1.1](#)).
- Intercurrent events and missing data: Serology data deemed unevaluable because of noncompliance with the key protocol criteria will be excluded. Missing data will not be imputed.
- Reporting results: The adjusted GMR and 2-sided 95% CI will be calculated based on the primary approach using a linear regression model that includes vaccine group, age group, and corresponding baseline strain-specific HAI (or H3N2-neutralizing antibody) titers as factors. The unadjusted GMR and the associated 2-sided 95% CI will also be provided.

6.2. Secondary Endpoints

6.2.1. Secondary BNT162b2 Immunogenicity Endpoints

6.2.1.1. Full-Length S-Binding IgG Levels

6.2.1.1.1. Main Analysis

- Estimands:
 - a. GMCs of full-length S-binding IgG levels before vaccination and 1 month after vaccination with BNT162b2 ([Section 2.1](#)).

- b. GMFRs of full-length S-binding IgG levels and SARS-CoV-2 neutralizing titers from before vaccination to 1 month after vaccination with BNT162b2 ([Section 2.1](#)).
- Analysis set: Evaluable BNT162b2 immunogenicity population, all-available immunogenicity population (as applicable) ([Section 4](#)).
- Analysis time point: Before vaccination (Visit 1 for the coadministration group and Visit 2 for the separate-administration group) and 1 month after vaccination with BNT162b2.
- Analysis methodology: The GMCs and the associated 2-sided 95% CIs at before vaccination and 1 month after vaccination with BNT162b2 will be provided for each vaccine group using the statistical methods described in [Section 5.2.2.2](#). The GMFRs and the associated 2-sided 95% CIs from before vaccination to 1 month after vaccination with BNT162b2 will be provided for each vaccine group using the statistical methods described in [Section 5.2.2.3](#).
- Intercurrent events and missing data: Serology data deemed unevaluable because of noncompliance with the key protocol criteria will be excluded. Missing data will not be imputed.
- Reporting results: GMCs and the associated 2-sided 95% CIs will be provided for each vaccine group at before vaccination and 1 month after vaccination with BNT162b2. GMFRs from before vaccination to 1 month after vaccination with BNT162b2 and the associated 2-sided 95% CIs will be provided for each vaccine group.

6.2.1.2. SARS-CoV-2 Neutralizing Titers (for a Subset of Approximately 200 Participants)

6.2.1.2.1. Main Analysis

Analyses for SARS-CoV-2 neutralizing titers are similar to those for full-length S-binding IgG levels described in [Section 6.2.1.1.1](#).

6.2.2. Secondary SIIV Immunogenicity Endpoint – Strain-Specific HAI (or H3N2-Neutralizing Antibody) Titers

6.2.2.1. Main Analysis

- Estimands:
 - a. GMTs of the strain-specific HAI (or H3N2-neutralizing antibody) titers before vaccination and 1 month after vaccination with SIIV ([Section 2.1](#)).
 - b. GMFRs of the strain-specific HAI (or H3N2-neutralizing antibody) titers from before vaccination to 1 month after vaccination with SIIV ([Section 2.1](#)).

- Analysis set: Evaluable SIIV immunogenicity population, all-available immunogenicity population (as applicable) ([Section 4](#)).
- Analysis time point: Before vaccination (at Visit 1) and 1 month after vaccination with SIIV.
- Analysis methodology: The GMTs and the associated 2-sided 95% CIs at before vaccination and 1 month after vaccination with SIIV will be provided for each vaccine group using the statistical methods described in [Section 5.2.2.2](#). The GMFRs and the associated 2-sided 95% CIs from before vaccination to 1 month after vaccination with SIIV will be provided for each vaccine group using the statistical methods described in [Section 5.2.2.3](#).
- Intercurrent events and missing data: Serology data deemed unevaluable because of noncompliance with the key protocol criteria will be excluded. Missing data will not be imputed.
- Reporting results: GMTs and the associated 2-sided 95% CIs will be provided for each vaccine group at before vaccination and 1 month after vaccination with SIIV. GMFRs from before vaccination to 1 month after vaccination with SIIV and the associated 2-sided 95% CIs will be provided for each vaccine group.

6.3. Other Endpoints

6.3.1. Exploratory Endpoints

6.3.1.1. Strain-Specific HAI Titers $\geq 1:40$ 1 Month After Vaccination With SIIV

6.3.1.1.1. Main Analysis

- Estimand: Percentage of participants with strain-specific HAI titers $\geq 1:40$ 1 month after vaccination with SIIV ([Section 2.1](#)).
- Analysis set: Evaluable SIIV immunogenicity population, all-available immunogenicity population (as applicable) ([Section 4](#)).
- Analysis time point: 1 Month after vaccination with SIIV.
- Analysis methodology: For each influenza strain, counts, percentages, and the associated 2-sided Clopper-Pearson 95% CIs of participants with strain-specific HAI titers $\geq 1:40$ 1 month after vaccination with SIIV will be provided for each vaccine group using the statistical methods described in [Section 5.2.1](#).
- Intercurrent events and missing data: Serology data deemed unevaluable because of noncompliance with the key protocol criteria will be excluded. Missing data will not be imputed.

- Reporting results: Counts, percentages, and the associated Clopper-Pearson 95% CIs will be provided for each vaccine group.

6.3.1.2. Strain-Specific HAI Seroconversion 1 Month After Vaccination With SIIV

6.3.1.2.1. Main Analysis

- Estimand: Percentage of participants with strain-specific HAI seroconversion 1 month after vaccination with SIIV ([Section 2.1](#)).

HAI seroconversion is defined as:

- a. an HAI titer $<1:10$ before SIIV vaccination and an HAI titer $\geq 1:40$ 1 month after SIIV vaccination or
 - b. an HAI titer $\geq 1:10$ before vaccination and a minimum 4-fold rise in HAI titer 1 month after SIIV vaccination.
- Analysis set: Evaluable SIIV immunogenicity population, all-available immunogenicity population (as applicable) ([Section 4](#)).
 - Analysis time point: 1 Month after vaccination with SIIV.
 - Analysis methodology: For each influenza strain, counts, percentages, and the associated 2-sided Clopper-Pearson 95% CIs of participants with strain-specific HAI titer seroconversion 1 month after vaccination with SIIV will be provided for each vaccine group using the statistical methods described in [Section 5.2.1](#).
 - Intercurrent events and missing data: Serology data deemed unevaluable because of noncompliance with the key protocol criteria will be excluded. Missing data will not be imputed.
 - Reporting results: Counts, percentages, and the associated Clopper-Pearson 95% CIs will be provided for each vaccine group.

6.3.1.3. H3N2 Neutralization Seroprotection/Seroconversion

6.3.1.3.1. Main Analysis

- Estimands:
 - Percentage of participants with H3N2 neutralization seroprotection 1 month after vaccination with SIIV.
 - Percentage of participants with H3N2 neutralization seroconversion 1 month after vaccination with SIIV.

Seroprotection for H3N2-neutralizing titers is defined as a neutralizing titer $\geq 1:80$.

Seroconversion for H3N2-neutralizing titers is defined based on prevaccination neutralizing titer:

- a. When prevaccination neutralizing titer is $< 1:20$, seroconversion is achieved if the postvaccination neutralizing titer is $\geq 1:80$.
 - b. When prevaccination neutralizing titer is $\geq 1:20$, seroconversion is achieved if the fold rise from the prevaccination neutralizing titer to the postvaccination neutralizing titer is ≥ 4 .
- Analysis set: Evaluable SIIV immunogenicity population, all-available immunogenicity population (as applicable) (Section 4).
 - Analysis time point: 1 Month after vaccination with SIIV.
 - Analysis methodology: Counts, percentages, and the associated 2-sided Clopper-Pearson 95% CIs of participants with H3N2 neutralization seroprotection and seroconversion 1 month after vaccination with SIIV will be provided for each vaccine group using the statistical methods described in Section 5.2.1.
 - Intercurrent events and missing data: Serology data deemed unevaluable because of noncompliance with the key protocol criteria will be excluded. Missing data will not be imputed.
 - Reporting results: Counts, percentages, and the associated Clopper-Pearson 95% CIs will be provided for each vaccine group.

CCI

